7.9 Reporting of AE/UP by the Study PI

The Study PI (or designee) will:

- Report to COH IRB and DSMC all reportable AEs that meet COH IRB and DSMC reporting criteria and occur at non-COH sites according to City of Hope’s Institutional policy on reporting AE/UP and indicate whether or not a protocol and/or consent form change is required.
- Report all expedited reportable AEs to participating investigators as an IND Safety Report occurring within 15 calendar days of receipt of sponsor (lead site) notification, and indicate

whether or not a protocol and/or consent form change is required. A cover letter will indicate the protocol title, the IND#, whether the FDA was informed, and, for non-COH sites, a statement that the report should be submitted to their local IRB for review as an IND safety report if applicable per local IRB policy.

- For IND Sponsor reporting purposes only: using a MedWatch 3500A form, report to the FDA, (via COH Office of IND Development and Regulatory Affairs (OIDRA)) regardless of the site of occurrence, any SAE that meets the FDA's criteria for expedited reporting following the reporting requirements and timelines set by the FDA:

Serious Adverse Events meeting the requirements for expedited reporting to the Food and Drug Administration (FDA), as defined in [21 CFR 312.32](#), will be reported as an IND safety report using the [MedWatch Form FDA 3500A for Mandatory Reporting](#).

The criteria that require reporting using the MedWatch 3500A are:

- Any unexpected fatal or life threatening adverse experience associated with use of the drug must be reported to the FDA no later than 7 calendar days after initial receipt of the information [\[21 CFR 312.32\(c\)\(2\)\]](#)
- Any adverse experience associated with use of the drug that is both serious and unexpected must be submitted no later than 15 calendar days after initial receipt of the information [\[21 CFR 312.32\(c\)\(1\)\]](#)
- Any follow-up information to a study report shall be reported as soon as the relevant information becomes available. [\[21 CFR 312.32\(d\)\(3\)\]](#)

The PI or designee will be responsible for contacting the Office of IND Development and Regulatory Affairs (OIDRA) at COH to ensure prompt reporting of safety reports to the FDA. OIDRA will assist the PI with the preparation of the report and submit the report to the FDA in accordance with the approved [City of Hope's Institutional policy](#).

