Given the prior toxicity experiences in AETHERA trial and the differences in treatment [32], in this study we will specifically monitor the occurrence of any "**unacceptable AE**". **Unacceptable AE** is defined as any of the following AEs that is at least **possibly attributed** to protocol therapy during treatment and safety follow-up:

- Any \geq Grade 3 immune-related AE
- Grade 3 fatigue or non-irAE skin toxicity that does not resolve within 7 days to \leq Grade 1/baseline
- Any other \geq Grade 3 non-hematologic non-irAE that does not improve within 3 days to \leq Grade 1/baseline as applicable with supportive care with the following **exception**:
 - \geq Grade 3 laboratory abnormality that is not clinically significant
- Grade 4 neutropenia that does not resolve to \leq Grade 2 within 3 days with supportive care (e.g. GCSF)
- Grade 3 or 4 thrombocytopenia with bleeding
- Any Grade 5 AE

This specific monitoring will be performed according to the rule below, which is based on the 50% quartile of the binomial distribution with an unacceptable toxicity rate of 33%.

- 3 or more patients with unacceptable toxicities when \leq 9 patients have been treated.
- 5 or more patients with unacceptable toxicities when \leq 16 patients have been treated.
- 8 or more patients with unacceptable toxicities when \leq 23 patients have been treated.
- 11 or more patients with unacceptable toxicities when \leq 33 patients have been treated.
- 15 or more patients with unacceptable toxicities when \leq 46 patients have been treated.

- 19 or more patients with unacceptable toxicities when ≤ 59 patients have been treated.

If the monitoring rule is met, the study PMT will review and assess the safety of the trial and submit a report outlining the findings and proposed action plans if any to the COH DSMC. The COH DSMC will review and make the decision to continue, modify, or permanently suspend accrual to the trial. At the end of the study with 59 evaluable participants, the 95% exact binomial confidence interval for the rate of such unacceptable AE will have a width of no more than 27%.

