15.7 City of Hope Data and Safety Monitoring Committee (DSMC)

This is a Risk Level 4 study, as defined in the City of Hope Data and Safety Monitoring Plan because the trial involves a COH IND.

The DSMC is a multidisciplinary committee charged with overseeing the monitoring of safety of participants in clinical trials, and the conduct, progress, validity, and integrity of the data for all clinical trials that are sponsored by City of Hope. The committee is composed of clinical specialists with experience in oncology and who have no direct relationship with the study. The committee reviews the progress and safety of all active research protocols that are not monitored by another safety and data monitoring committee or board.

The COH DSMC will review and monitor toxicity and accrual data from this trial. Information that raises any questions about participant safety will be addressed with the Principal Investigator, statistician and study team. The COH DSMC Charter is a supplement to this protocol.

The DSMC will review the study's status every 3 months and/or more frequently if necessary. The DSMC will review up-to-date participant accrual; summary of all adverse events captured via routine and expedited reporting; a summary of deviations; any response information; monitoring reports, and summary comments provided by the study team. Other information (e.g. scans, laboratory values) will be provided upon request. A review of outcome results (response, toxicity and adverse events) and factors external to the study (such as scientific or therapeutic developments) is discussed, and the Committee votes on the status of each study.

Data and safety will be reported to the COH DSMC using the PMT report and submitted every 3 months from the date of activation.

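### The toxicity monitoring rule has no event-driven trigger for a treatment-related death: such a death counts as one ordinary unacceptable AE against boundaries built on a 33% composite rate

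*Combined protocol and SAP*

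**What the plan says.** Section 12.3.3 and the Toxicity Monitoring part of the synopsis define an unacceptable AE as any of six kinds of event at least possibly attributed "to protocol therapy during treatment and safety follow-up". Fatal AEs are the last of the six. They have no weight or limit of their own.

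Patients with any of the six are counted together. The boundaries are "based on the 50% quartile of the binomial distribution with an unacceptable toxicity rate of 33" per cent. They run from "3 or more patients with unacceptable toxicities when" up to 9 have been treated and "5 or more patients with unacceptable toxicities when" up to 16 have been treated, through 8 of 23, 11 of 33 and 15 of 46, to "19 or more patients with unacceptable toxicities when" up to 59 have been treated.

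The consequence is stated: "If the monitoring rule is met, the study PMT will review and assess the safety of the trial" and reports to the DSMC, which then decides whether accrual continues, is modified or is suspended.

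Other sections also deal with deaths:
- Section 7.1 and Table 7.8.2: death is an SAE, and SAEs from Day 1 through the 100-day visit go to the DCC and Study PI within 24 hours.
- Section 7.9: the Study PI is to "Report to COH IRB and DSMC all reportable AEs that meet COH IRB and DSMC reporting criteria", to report unexpected fatal events to the FDA within 7 days, and to send the DSMC a PMT report every 3 months.
- Section 15.4: the PMT meets at least monthly and addresses whether further enrolment is appropriate.
- Section 15.7: "The DSMC will review the study's status every 3 months and/or more frequently if necessary", and the committee votes on the study's status.

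**The concern.** The rule is the one place where the protocol fixes in advance how many bad outcomes prompt a safety report and a decision on accrual. Its benchmark of 33% belongs to a mixed set of mostly non-fatal toxicities. The experience that 12.3.3 cites in support consists of Grade 3-4 event rates from AETHERA (56% with at least one). No fatal-event rate appears there, so nothing in the documents supports 33% as a yardstick for death.

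Fatal toxicity is foreseeable here. The nivolumab table in 6.1.2 marks several reactions, pneumonitis and myocarditis among them, as having had fatal cases. A sponsor would normally want a possibly related death in a consolidation trial to prompt its own review, and this rule does not provide for that. At the planned 2 to 3 patients a month, 6 to 9 more could start treatment between two quarterly DSMC reviews (3 × 2 = 6; 3 × 3 = 9).

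**Working it through.** **1. Reproduce the boundaries.** The inputs are the 33% rate and the cut-offs 9, 16, 23, 33, 46 and 59 from 12.3.3. The medians of Binomial(n, 0.33) at those n are 3, 5, 8, 11, 15 and 19, exactly as stated. The stated precision also holds: the widest exact 95% interval at n = 59 is 26.6 percentage points, within the 27% given.

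**2. Largest counts below each boundary.** These are 2/9 (22%), 4/16 (25%), 7/23 (30%), 10/33 (30%), 14/46 (30%) and 18/59 (31%). If all were deaths, the exact 95% intervals for the first two would be 2.8% to 60.0% and 7.3% to 52.4%.

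**3. Condition on the 16-patient case.** Two deaths in 9 are below every boundary, so that statement is unconditional. Four deaths in 16 are below 5, but three of them occurring while 9 or fewer had been treated would already have met the first boundary. If all placements of four events among 16 patients are equally likely, the number with three or four in the first 9 is C(9,3) × 7 + C(9,4) = 588 + 126 = 714, out of C(16,4) = 1820, or 39%. The four-death case therefore escapes the rule only if no more than two fell in that first stage.

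**4. Chance that deaths alone ever meet the rule.** The documents give no treatment-related death rate, so p is assumed. Patients are taken as independent, with each outcome known as soon as the patient is counted. Most of the probability comes from the first boundary:

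P(3 or more in 9) = 1 − (1−p)^9 − 9p(1−p)^8 − 36p²(1−p)^7

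At p = 0.05 this is 1 − 0.6302 − 0.2985 − 0.0629 = 0.0084. An exact recursion through all six boundaries raises it to 0.0087. The chance of at least one death in 59 is 1 − (1−p)^59, and the expected number is 59p.

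| Assumed p | 3 or more in 9 | Deaths alone ever meet rule, 59 patients | At least one death in 59 | Expected deaths |
|---|---|---|---|---|
| 2% | 0.06% | 0.06% | 70% | 1.2 |
| 5% | 0.84% | 0.9% | 95% | 3.0 |
| 10% | 5.3% | 5.9% | 99.8% | 5.9 |

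At 20% the rule would be met by deaths alone with probability 33%. Checking after every patient or only at the six cut-offs gives the same figures. Any delay before a death is known moves it towards a later, higher boundary, so these probabilities would fall and not rise.

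**5. What other events add.** Suppose two of the first 9 have died and the other 7 each have a non-fatal unacceptable AE with probability q (assumed). The rule is then met with probability 1 − (1−q)^7, which is 52%, 79% and 92% at q = 10%, 20% and 30%.

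**The case against.** The strongest reply is that deaths are already escalated faster than any count could manage, and that the bodies named in 12.3.3 already have to act on them. This largely stands. A reader might infer that the composite count alone obliges the PMT to report and the DSMC to decide on accrual. The documents do not support that. Section 7.9 requires a PMT report every 3 months, 15.4 has the PMT consider further enrolment at least monthly, and 15.7 has the DSMC vote on the study at least quarterly and sooner if necessary. The DSMC charter and the institutional reporting criteria, which may already call for prompt review of a related death, are not in these documents.

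A second reply is that deaths never stand alone in the count. That is also right: step 5 shows that two early deaths leave the rule one event short, and that event may well be present. So it would be too strong to say that the rule cannot respond when patients die. It would also be wrong to read 33% as a death rate the plan tolerates, because the plan offers it only for the composite. Nor is meeting the rule a halt. It leads to a review and a decision.

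What remains is narrower. Whether the 12.3.3 sequence starts after a related death depends on how many unrelated kinds of toxicity have also occurred. The alternatives run on a calendar or on a judgement that earlier review is necessary. No section of the protocol makes the death itself the trigger.

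**Conclusion.** The point holds as a gap in the event-driven rule, not in the oversight system as a whole. Two treatment-related deaths in the first 9 patients, or four in the first 16 with no more than two in the first stage, would not by themselves start the PMT report and DSMC decision of 12.3.3. Over the full 59 patients, deaths alone would start it with probability 0.06%, 0.9% or 5.9% at true rates of 2%, 5% or 10%. Those rates are assumptions, since the documents give none, and the figures deliberately leave out other unacceptable AEs, which would make the rule easier to meet. The boundaries are correctly calculated, and nothing here affects the efficacy test or the sample size. This is an inexpensive improvement to a design choice. If the charter already provides for it, the change only makes that visible in the protocol.

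**What to change.** Add one sentence to 12.3.3 and to the synopsis, for example: *Any Grade 5 AE at least possibly attributed to protocol therapy meets the monitoring rule on its own and prompts the PMT report and DSMC review described below.* Leave the six composite boundaries and the DSMC's discretion over accrual as they are.

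The cost is some unscheduled reviews. If each such death prompts one, the expected number over 59 patients is 59 × 0.02 = 1.2, 59 × 0.05 = 3.0 or 59 × 0.10 = 5.9 at the three assumed rates. The number is small if such deaths are rare and grows only if they are not, which is when the reviews are wanted.

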13.0 DATA HANDLING, DATA MANAGEMENT, RECORD KEEPING

13.1 Source Documents

Source documents are original documents, data, and records (e.g., medical records, pharmacy dispensing records, recorded data from automated instruments, laboratory data) that are relevant to the clinical trial. The Site Investigator or their designee will prepare and maintain adequate and accurate source documents. These documents are designed to record all observations and other pertinent data for each patient enrolled in this clinical trial. Source documents must be adequate to reconstruct all data transcribed onto the case report forms.

13.2 Data Capture Methods and Management

Data for this trial will be collected using Medidata RAVE, City of Hope's electronic capture system. Medidata RAVE is a web based, password protected system that is fully compliant with global regulatory requirements, including 21CRF Part 11 compliant.

13.3 Case Report Forms/ Data Submission Schedule

Study personnel at each site will enter data from source documents corresponding to a participant's visit into the protocol-specific electronic Case Report Form (eCRF) when the information corresponding to that visit is available.

The investigator is responsible for all information collected on participants enrolled in this study. All data collected during the course of this study must be reviewed and verified for completeness and accuracy by the investigator. All case report forms must be completed by designated study personnel. The completed case report forms must be reviewed, signed and dated by the Site Investigator or designee in a timely fashion.

All data will be collected using electronic data collection system described in [Section 13.2](#), and will be submitted according to the timelines indicated in [Table 13.3](#).

Table 13.3 Data Submission Schedule

Form	Submission Timeline
Eligibility Checklist	Complete prior to registration
On Study Forms	Within 14 calendar days of registration
Baseline Assessment Forms	Within 14 calendar days of registration
Treatment Forms	Within 14 calendar days of treatment administration
Adverse Event Report Forms	Within 10 calendar days of the assessment/notification
Response Assessment Forms	Within 10 calendar days of the response assessment
Other Assessment Forms	Within 10 calendar days of the assessment
Off Treatment/Off Study Forms	Within 10 calendar days of completing treatment or being taken off study for any reason
Follow up/ Survival Forms	Within 14 calendar days of the protocol defined follow up visit date or call

13.4 Regulatory Records

The investigator will maintain regulatory records, including updating records in accordance with Good Clinical Practice guidelines and FDA regulations.

14.0 ADHERENCE TO THE PROTOCOL

A deviation is a divergence from a specific element of a protocol that occurred without prior IRB approval.

It is understood that deviations from the protocol should be avoided, except when necessary to eliminate an immediate hazard to a research participant. Protocol deviations may be on the part of the participant, the investigator, or study staff.

All deviations from the protocol must be documented in study participant source documents and promptly reported to the Study PI and to the local IRB according to its policies requirements. The Study PI will report the deviation according to City of Hope's deviation policy for reporting deviations.

14.1 Emergency Modifications

Investigators may implement a deviation from the protocol to eliminate an immediate hazard(s) for the protection, safety, and well-being of the study patient to trial participants without prior IRB or Sponsor approval.

For any such emergency modification implemented:

- The local IRB and/or DSMC must be notified according to local institutional policies.
- The Study PI must be notified as soon as practicable (within 24 hours) via email to the Study PI and [contact]. This email should provide input on the following:
 - Description of the event
 - Impact on participant safety or the safety to others
 - Impact on the study design

14.2 Planned Non-Emergency Deviations

All non-emergency planned deviations from the protocol must have prior approval by the Study PI, the Site Lead Investigator and the local IRB, and if applicable the COH IRB.

14.3 Unplanned Deviations – Deviations Discovered After They Have Occurred.

For deviations to the protocol discovered after they have occurred:

- The local IRB and/or DSMC must be notified according to local institutional policies.
- The Study PI must be notified as soon as practicable (within 24 hours of awareness of event) via email to the Study PI and [contact]. This email should provide input on the following:
 - Description of the event
 - Impact on participant safety or the safety to others
 - Impact on the study design
 - A corrective and preventative action plan

A list of deviations from all participating sites will be submitted along with the Protocol Management Team (PMT) progress report to the COH DSMC.

14.4 Single Subject Exceptions

An SSE is a planned deviation, meaning that it involves circumstances in which the specific procedures called for in a protocol are not in the best interests of a specific patient. It is a deviation that is anticipated and receives prior approval by the PI and the IRB.

COH only: Reporting SSEs: the SSE must be submitted as a “Single Subject Exception Amendment Request” via iRIS in accordance with IRB guidelines and the [Clinical Research Protocol Deviation policy](#). An IRB approved SSE does not need to be submitted as a deviation to the DSMC.

15.0 STUDY OVERSIGHT, QUALITY ASSURANCE, AND DATA & SAFETY MONITORING

15.1 Site Lead Investigator Responsibilities

The Site Lead Investigator is responsible for the conduct of the clinical trial at the site in accordance with Title 21 of the Code of Federal Regulations (CFR). The Site Lead Investigator must assure that all study site personnel, including sub-investigators and other study staff members, adhere to the study protocol and all FDA/GCP/NCI regulations and guidelines regarding clinical trials both during and after study completion.

It is the responsibility of the Site Lead Investigator to oversee the safety of the study at his/her site. This safety monitoring will include careful assessment and appropriate reporting of adverse events, deviations, and unanticipated problems.

The Site Lead Investigator will be responsible for assuring that all the required data will be collected and entered onto the Case Report Forms at his/her site. For remote or onsite monitoring and auditing, the Site Lead Investigator will provide access to his/her original records to permit verification of proper entry of data. At the completion of the study, all case report forms will be reviewed by the Site Lead Investigator and will require his/her final signature to verify the accuracy of the data.

An investigator is responsible for ensuring that an investigation is conducted according to the signed investigator statement, the investigational plan, and applicable regulations; for protecting the rights, safety, and welfare of participants under the investigator's care; and for the control of drugs under investigation.

15.2 All Investigator Responsibilities

All investigators agrees to:

- Conduct the study in accordance with the protocol and only make changes after notifying the Sponsor (or designee), except when necessary to protect the safety, rights or welfare of subjects.
- Personally conduct or supervise the study (or investigation).
- Ensure that the requirements relating to obtaining informed consent and IRB review and approval meet federal guidelines, as stated in § 21 CFR, parts 50 and 56.
- Report to the Sponsor or designee any AEs that occur in the course of the study, in accordance with §21 CFR 312.64.
- Ensure that all associates, colleagues and employees assisting in the conduct of the study are informed about their obligations in meeting the above commitments.
- Maintain adequate and accurate records in accordance with §21 CFR 312.62 and to make those records available for inspection with the Sponsor (or designee).
- Ensure that an IRB that complies with the requirements of §21 CFR part 56 will be responsible for initial and continuing review and approval of the clinical study.
- Promptly report to the IRB and the Sponsor all changes in the research activity and all unanticipated problems involving risks to subjects or others (to include amendments and IND safety reports).
- Seek IRB and Sponsor approval before any changes are made in the research study, except when necessary to eliminate hazards to the patients/subjects.

- Comply with all other requirements regarding the obligations of clinical investigators and all other pertinent requirements listed in § 21 CFR part 312.

15.3 Study PI Responsibilities

The Study PI is responsible for the conduct of the clinical trial, including overseeing that sponsor responsibilities as defined in § 21 CFR 312.

15.4 Protocol Management Team (PMT)

The PMT minimally consisting of the Study Principal Investigator, Site Lead Investigator(s), collaborating investigators, the research nurse, the clinical research associate/coordinator, and the study biostatistician is responsible for ongoing monitoring of the data and safety of this study.

The PMT will meet (in person or via teleconference) at least monthly, and will meet at least quarterly with the study biostatistician, to review study status. This review will include, but not be limited to, reportable AEs and UPs, and an update of the ongoing study summary that describes study progress in terms of the study schema. The meeting will be a forum to discuss study related issues including accrual, SAE/AEs experienced, study response, deviations/violations and study management issues. The appropriateness of further subject enrollment and the specific intervention for subsequent subject enrollment are addressed, including the implementation of stopping rules.

